## **9. Analysis plan**

All analyses will be performed using intention-to-treat. Data can be missing for any day if the participant did not use the activity tracking device or did not upload data. For the main analysis, we will use multiple imputation for step values that are either missing or for values less than 1000 steps because evidence suggests these are not accurate measures of actual activity. We will perform five sets of imputations and results will be combined using Rubin's standard rules. We will perform sensitivity analyses to assess the robustness of the findings using only collected data with and without step values less than 1000 steps.

The primary analysis will fit mixed effects regression models to evaluate changes in physical activity outcomes measures adjusting for each participant's baseline step, time at the observation level using calendar month fixed effects, participant random effects, and adjusting for repeated observations of participant step counts. We will compare changes from baseline to the intervention period (excluding weeks 1 to 4 during the ramp-up phase) and from baseline to the follow-up period. Secondary analyses will fit mixed effects regression models adjusted for other variables of interest such as participant characteristics. Exploratory analyses will fit mixed effects regression models to evaluate associations of participant characteristics or behaviors with strong or poor performance in the outcome measures. We will also conduct an exploratory qualitative evaluation of the survey free text responses.

This study has been powered for two phases of hypothesis testing. In the first phase, we will compare each of the three intervention arms to control. We estimate that a sample of 600 participants allocated in a 1:1:1:1 distribution, will ensure at least 80% power to detect an 800 step difference between each intervention arm and control, with a standard deviation of 2000 steps. This calculation assumes a 10% dropout rate and a conservative Bonferroni adjustment of the type I error rate with a 2-sided alpha of 0.017. In the second phase, we will compare successful intervention arms to each other. We expect that the magnitude of difference between intervention arms will be less than that of successful intervention arms compared to control. For this second phase of analyses will use a conservative Bonferroni adjustment of the type I error rate with a 2-sided alpha of 0.017 to adjust for up to 3 comparisons. Because only intervention arms which demonstrated a significant difference with the control are compared with each other in the second phase, the overall familywise error rate of this two-phase procedure is controlled at 0.05.

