## **7. Subject compensation**

All participants will receive \$25 to enroll in the study (defined as being randomized and starting the intervention), \$50 for completing the 24-week intervention and surveys, and \$50 for completing the entire 36-week study.

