## *11.6 Risk/benefit*

### *11.6.1 Potential study risks*

To minimize the chance for serious and unexpected adverse events, study participants will be screened through exclusion criteria for any health conditions that may be exacerbated by participating in a physical activity study. The program will use a gradual increase in physical activity during the first month that should pose little health risk to participants. Participants are given guidance on when to seek medical attention and a reporting protocol is in place to capture any changes in symptoms with physical activity. Another potential risk of this study is a breach of participant confidentiality. We will minimize this risk by using secure data methods as described previously. Due to the financial incentives in this study, we will be collecting social security numbers so that we can complete W-9 forms for participants. Social security numbers only will be used to generate W-9 forms and will be deleted once they are no longer needed. We will also collect home addresses to mail incentive payments. This will be done through a University of Pennsylvania approved partnership with Wells Fargo. Accidental disclosure of social security numbers could lead to identity theft. We will use commercial-grade encryption to protect social security information in transit. Names and addresses will be stored in encrypted databases. These data will be viewable only by the respective participants, the study coordinator(s) and the project manager(s). All other members of the research team will be able to view only participant ID numbers. Even the study arms will be identified by code letters until both the statistician and PI agree that analysis is complete.

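### Minor: raising the number of imputations from five to 50 would remove most of the avoidable seed noise in borderline results at the 0.017 gate, at the cost of computing time only

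*Combined protocol and SAP*

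**What the plan says.** Section 9 (Analysis plan) explains how gaps arise: "Data can be missing for any day if the participant did not use the activity tracking device or did not upload data". Days with no value and days below 1000 steps are both multiply imputed for the main analysis, and "We will perform five sets of imputations and results will be combined" by Rubin's rules. The section gives no seed, imputation model, expected amount of missing data or check of simulation error. The primary model adjusts for baseline steps and calendar month, with "participant random effects, and adjusting for repeated observations of participant step counts".

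The sensitivity analyses are run "using only collected data with and without step values less than 1000 steps".

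Sections 5.4 and 9 set two-sided alpha at 0.017 for each contrast with control and state at least 80% power for 800 steps (SD 2000, 600 participants, equal allocation). On attrition, "This calculation assumes a 10% dropout rate". The first-phase tests act as a gate, because "only intervention arms which demonstrated a significant difference with the control are compared with each other in the second phase".

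**The concern.** A multiply imputed estimate depends partly on the random draws. With few imputations, two analysts who use the same data and model but different seeds can obtain different p-values. This matters more than usual here because crossing 0.017 decides both the arm's own result and whether the arm enters phase two. A chance flip at the first gate can therefore also change which arms are compared later. Unlike sampling error, this noise can be reduced without recruiting anyone.

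A second, optional matter is that non-wear and non-upload are participant behaviors. Unrecorded days may therefore differ from recorded days in ways the model does not capture, and no planned analysis shows how large such a difference would have to be to change a conclusion.

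**Working it through.** **Reproducing the plan's figure.** The inputs from sections 5.4 and 9 are SD 2000, difference 800, two-sided alpha 0.017 (z = 2.387), 80% power (z = 0.842), 10% dropout and 150 per arm.

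- n per arm = 2 × (2000/800)² × (2.387 + 0.842)² = 130.3, so 131. Then 131/0.90 = 145.6, so 146 per arm and 584 in total, against 600 planned.
- With 135 per arm, SE = 2000 × √(2/135) = 243.4 and power = Φ(800/243.4 − 2.387) = 81.6%. The stated power reproduces.

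**Range for FMI (assumed).** FMI is the share of the contrast's variance that is due to missing data.

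- *Upper end, 10%.* This treats the planned 10% dropouts as contributing nothing.
- *Lower end, about 1%.* This is for scattered missing days. There are 140 days in weeks 5 to 24. Assume a within-person day SD s of 2000 to 4000, independent days and a missing share f. The added variance is A = (s²/140) × f/(1 − f), and FMI = A/(2000² + A). This gives 0.08% to 0.32% at f = 10% and 0.3% to 1.2% at f = 30%. Long gaps or correlated days would raise it.

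**Size of the seed noise.** Complete-data variance W = 2000² × 2/150 = 53,333 (SE 230.9). With unlimited imputations the variance is T = W/(1 − FMI), and the between-imputation part is B = FMI × T. The seed SD of the pooled difference with m imputations is √(B/m). At FMI 10%, T = 59,259 and B = 5,926, so the seed SD is 34.4 steps with five and 10.9 with 50.

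**Effect on the decision.** The pooled estimate was simulated with variance T + B/m, an estimated B distributed as B × χ²(m−1)/(m−1), total variance W + (1 + 1/m) × estimated B, and Rubin's degrees of freedom. The true effect was 800 steps. The table shows how often two seeds on the same data disagree at 0.017 for one contrast:

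| FMI | 5 imputations | 20 | 50 |
|---|---|---|---|
| 1% | 1.2% | 0.6% | 0.4% |
| 5% | 3.2% | 1.5% | 0.9% |
| 10% | 5.7% | 2.5% | 1.5% |

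- *Validity.* Type I error with five is about 0.017 at each FMI.
- *Power.* At FMI 10% it is about 80% with five and 81.5% with 50. At FMI 1% the loss from using five is about 0.1 percentage point.
- *Dependence on the true effect (FMI 10%, five imputations).* Disagreement is 0.9% at no effect, 8.1% at 600 steps, 2.1% at 1000 and 0.4% at 1200.
- *Dependence on the p-value (FMI 10%).* Call the p-value from unlimited imputations the limiting p. A limiting p of 0.010 passes 0.017 in 80% of seeds with five and over 99.9% with 50; a limiting p of 0.025 passes in 15% and 0.2%. A limiting p of 0.005 already passes in 97% with five, and 0.001 in over 99.9%.
- *Spread at the threshold.* A limiting p of 0.017 ranges (central 95%) over 0.007–0.045 with five and 0.013–0.022 with 50 at FMI 10%. At FMI 1% the ranges are 0.013–0.022 and 0.016–0.018.
- *Phase-two set.* If all three arms truly have an 800-step effect, the set of arms passing the gate differs between two seeds in 3.4% (five) against 1.1% (50) of trials at FMI 1%, and in 15.8% against 4.4% at FMI 10%.

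**Optional point: tipping shift.** Suppose the observed effect is 800 steps and only the intervention arm's imputed days are shifted. The shift that removes significance is (800 − 2.387 × SE)/share of days imputed, with SE = 230.9/√(1 − FMI).

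- FMI equal to the share (10% / 20% / 30%): SE 243.4 / 258.2 / 276.0, margin 219 / 184 / 141, shift about 2190 / 920 / 470 steps.
- FMI 1%: SE 232.1, margin 246, shift about 2460 / 1230 / 820 steps.

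**The case against.** The strongest reply is that nothing here is an error. Section 9 names a number of imputations and a valid pooling rule, and no other text contradicts it. A reader might infer that five imputations inflate the false-positive rate or break the 80% power claim; neither follows, as the type I error and power figures show. At FMI 10%, five imputations add only B/5 = 1,185 to a variance of 59,259, or 2%. This objection stands and is why the point is minor.

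The size also rests on an FMI that the documents do not give. For the day-by-day gaps that section 9 describes, about 1% is plausible and the effect is small. The 15.8% figure needs both the top of the range and a true 800-step effect in all three arms. This stands too, so the result is given as a range.

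A reader might suspect that a favorable seed could be chosen. Section 11.6.1 limits that: "Even the study arms will be identified by code letters until both the statistician and PI agree that analysis is complete". Coding does not reduce random seed noise, however.

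On the optional point, a reader might infer that the sensitivity analyses leave the handling of unrecorded days unchanged. They do change it: those days are left out instead of imputed. What is absent is narrower, namely an analysis that lets unrecorded days differ systematically from recorded ones given the model. Nor do the documents show that missingness will differ by arm or that it is non-ignorable. They state no imputation model, and section 7 pays every arm equally "for completing the 24-week intervention and surveys". Baseline adjustment and participant random effects reduce the worry further. These safeguards lessen the case for the extra analysis without removing it.

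**Conclusion.** The point holds as a minor improvement in precision and reproducibility. Moving from five to 50 imputations cuts two-seed disagreement on a contrast by about two-thirds at FMI 1% (1.2% to 0.4%) and three-quarters at FMI 10% (5.7% to 1.5%). These figures assume a true 800-step effect, the plan's SD of 2000 and 150 randomized per arm. The benefit is confined to results near 0.017. Fifty imputations reduce seed dependence but do not abolish it: if the limiting p lies almost exactly at 0.017, no practical number settles the gate.

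The missing-not-at-random analysis is optional. With 10% of days imputed, a shift of more than 2000 steps per imputed day in one arm would be needed to overturn an observed 800-step effect, so such a result would be fairly robust. Robustness falls as the share rises, and the documents do not give the share.

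**What to change.** Replace the sentence on the number of imputations in section 9 with:

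> We will create 50 imputed data sets, with the random seed recorded before outcome data are analyzed, and pool the results by Rubin's rules.

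The larger number reduces the noise; recording the seed only makes the result repeatable. Twenty imputations would recover most of the gain. The cost is computing time and one sentence of wording.

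Optionally, keep both planned sensitivity analyses and add a delta-adjusted analysis of the primary contrasts:

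> For each intervention arm in turn, all imputed days in that arm (no recorded value, or a recorded value below 1000 steps) will be shifted, with control unshifted. We will report the share of imputed days by arm and the smallest shift that changes each conclusion at 0.017.

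This also needs no new data.

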### **--Randomization—**

Participants are considered ready to be randomized once they have completed all surveys, established a baseline step count, and selected a step goal increase.

Participants will be stratified on baseline step count (less than 5000 steps, 5001 to 7500 steps, or more than 7500 steps). Participants will then be randomly assigned within their strata in blocks of four groups, with each group having 3 participants. The first participant in the group will be randomly assigned to the arm and the next 2 participants will be assigned to fill that group. Then the next participant will be randomly assigned to an arm within that block and the following two participants will be assigned to fill that group, and so on until the block within the strata is filled of 4 groups, each with three participants per group.

Participants in all arms will be asked to complete a series of follow-up surveys the end of the 24-week intervention period and again at the end of the 12-week follow up period. The interventions within each arm are as follows:

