**--Arm 3: Competitive social incentive intervention--**

Participants in this arm will be in a group of three total participants. At the end of each week the participants will receive an email with a leaderboard that ranks them on their cumulative points in the study thus far and also displays their level. In the event there is a tie in total cumulative points, the participants will be secondarily ranked on level. This feedback may help to induce participants to compete for the top spot among the group.

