**--Arm 4: Collaborative social incentive intervention--**

Participants in this arm will be in a group of three total participants as a team. Each day one of the members of the group will be randomly selected to represent their team for that day. If the participant selected met his or her step goal on the previous day, the team keeps their points. If he or she didn't meet their goal, then the team loses 10 points. In this design, each person is accountable to the others on the team and this may induce a collaborative effort to meet their daily goals. The entire team moves up a level only if the team has at least 40 points by the end of the week.

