### *5.4 Accrual*

This study has been powered for two phases of hypothesis testing. In the first phase, we will compare each of the three intervention arms to control. We estimate that a sample of 600 participants allocated in a 1:1:1:1 distribution, will ensure at least 80% power to detect an 800 step difference between each intervention arm and control, with a standard deviation of 2000 steps. This calculation assumes a 10% dropout rate and a conservative Bonferroni adjustment of the type I error rate with a 2-sided alpha of 0.017. In the second phase, we will compare successful intervention arms to each other. We expect that the magnitude of difference between intervention arms will be less than that of successful intervention arms compared to control. For this second phase of analyses will use a conservative Bonferroni adjustment of the type I error rate with a 2-sided alpha of 0.017 to adjust for up to 3 comparisons. Because only intervention arms which demonstrated a significant difference with the control are compared with each other in the second phase, the overall familywise error rate of this two-phase procedure is controlled at 0.05.

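### Participants are assigned in threes and arms 3 and 4 link them, but the primary model has no group-level variance, so the power and familywise error statements rest on unstated independence

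*Combined protocol and SAP*

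**What the plan says.** **Assignment (section 5.1, Randomization).** Within baseline-step strata, each block holds four groups of three. Only the first member is randomised: the "first participant in the group will be randomly assigned to the arm and the next 2 participants will be assigned to fill that group". This applies to all four arms.

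**Links between members (section 5.1, Arms 3 and 4).** Arm 3 sends a weekly leaderboard to the three members, and the plan states its purpose: "This feedback may help to induce participants to compete for the top spot among the group". Arm 4 pools points and level: "The entire team moves up a level only if the team has at least 40 points by the end of the week". For arms 1 and 2 no contact between group members is described.

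**Primary model (section 9).** It adjusts for baseline steps and for "time at the observation level using calendar month fixed effects, participant random effects, and adjusting for repeated observations of participant step counts". On imputation: "We will perform five sets of imputations and results will be combined using" Rubin's rules. No group effect, group-clustered variance or group-based sensitivity analysis appears in any section.

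**Planning statements (sections 5.4 and 9, same text).** 600 participants "will ensure at least 80% power to detect an 800 step difference between each intervention arm and control", with SD 2000, 10% dropout and a "conservative Bonferroni adjustment of the type I error rate with a 2-sided alpha of 0.017". After phase 2, also at 0.017, the text concludes that "the overall familywise error rate of this two-phase procedure is controlled at 0.05". Neither statement mentions an ICC, a design effect or an assumption of independence.

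**The concern.** Where three people follow one random draw and then act on each other for 24 weeks, their outcomes may be correlated. In arms 3 and 4 that mutual influence is the mechanism under test. A model with participant random effects treats the roughly 135 to 150 people per arm as independent. If they are not, the standard error is wrong for any comparison involving arm 3 or 4. Positive correlation is plausible for a team and makes the tests reject too often. Negative correlation is possible under competition and makes them conservative. At stake are the per-comparison level of 0.017 and the familywise level of 0.05, both stated without conditions.

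**Working it through.** **Inputs from the documents.** 600 participants at 1:1:1:1, so 150 per arm; 10% dropout, so 135; difference 800; SD 2000; two-sided alpha 0.017 (z = 2.387); groups of three. **Assumed:** within-group ICC, written r, of 0.05 / 0.10 / 0.20, because the documents give none.

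**1. The plan's own figure.** Independent-participant formula: n = 2 × [2000 × (2.387 + 0.842) / 800]² ≈ 130.3, so 131 per arm; 131 / 0.9 gives 146 per arm, 584 in total, against 600 planned. At 135 per arm, SE = 2000 × √(2/135) = 243.4; 800 / 243.4 = 3.286; power = Φ(3.286 − 2.387) = 81.6%. The stated 80% reproduces with no allowance for groups.

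**2. Size of the planned test.** With intact triplets, the variance of a correlated arm's mean is multiplied by 1 + 2r. The variance of the difference is then multiplied by 1 + r against an uncorrelated arm, and by 1 + 2r for two correlated arms. The planned test still uses 243.4, so its true size is 2 × [1 − Φ(2.387 / √factor)]. At r = 0.10: 2.387 / √1.10 = 2.276 gives 0.023, and 2.387 / √1.20 = 2.179 gives 0.029.

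| | r = 0.05 | 0.10 | 0.20 |
|---|---|---|---|
| Arm 3 or 4 v control | 0.020 | 0.023 | 0.029 |
| Arm 3 v arm 4 | 0.023 | 0.029 | 0.044 |
| FWER, global null, arms 3 and 4 correlated | 0.051 | 0.056 | 0.068 |
| FWER, three equal interventions, all pass phase 1 | 0.054 | 0.064 | 0.086 |

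With 10% random dropout a member keeps on average 2 × 0.9 = 1.8 partners, so the factor is 1 + 1.8r. The first two rows become 0.020 / 0.022 / 0.028 and 0.022 / 0.028 / 0.041. At r = −0.10 with intact triplets they are 0.012 and 0.008.

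**3. Familywise error (FWER).** The FWER rows apply the two-phase rule with unclustered standard errors to simulated arm means. At r = 0 the FWER is about 0.045, so Bonferroni leaves slack of about 0.005. Across the two scenarios it stays at or below 0.05 up to a common r of about 0.03. If arms 1 and 2, also filled in threes, correlate as well, r = 0.10 in all four arms gives 0.076 under the global null. If arms 3 and 4 have opposite signs of equal size, the FWER stays below 0.05 only up to about 0.23: −0.25/+0.25 gives 0.051 and −0.40/+0.40 gives 0.059 under the global null.

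**4. Power at 800 steps, arm 3 or 4 v control.** Planned test: Φ[(3.286 − 2.387) / √(1 + r)]. Group-adjusted test with random dropout: Φ[3.286 / √(1 + 0.9r) − 2.387].

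| | r = 0 | 0.05 | 0.10 | 0.20 |
|---|---|---|---|---|
| Planned test, 135 per arm | 81.6% | 81.0% | 80.4% | 79.4% |
| Group-adjusted, 135 per arm, normal | 81.6% | 79.6% | 77.7% | 73.8% |
| Group-adjusted, 135 per arm, t on 98 df | 80.3% | 78.3% | 76.3% | 72.4% |
| Group-adjusted, all 150 per arm, normal | 85.9% | 84.0% | 82.0% | 78.1% |

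The planned test reaches 80% at r of about 0.14; the group-adjusted normal test at 135 per arm does so at about 0.04.

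**5. Does imputation change this?** Trials were simulated with 50 triplets per arm, 10% dropout, a further 15% of weeks missing and five imputations (20,000 trials per scenario; variance components treated as known; baseline and month terms omitted). At r = 0.10 and 0.20, the unclustered test had size 0.022–0.024 and 0.028–0.029 against control. Over r = −0.10, 0, 0.10 and 0.20, the group-clustered test had size 0.014–0.018 with group in the imputation model and 0.013–0.020 without it.

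**The case against.** **An arm that does nothing creates no correlation.** Groups are filled in order of readiness and the documents describe no prior tie between members. If arm 3 or 4 affects nobody, the intervention induces no dependence and the test against control keeps its size, apart from timing effects that the calendar-month terms partly absorb. This stands as a condition. The size error against control needs an arm that makes members move together, or apart, while leaving the mean unchanged. Arm 3 against arm 4 needs no such condition, because both may work equally well and still correlate members.

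**The ICC is unknown and the groups are small.** True, and nothing in the documents places the trial within the assumed range. The second FWER row is also a limiting case in which all three interventions are sure to pass phase 1. With a true effect of exactly 800 steps in each and ICC 0.10 in arms 3 and 4, the chance of a false phase 2 claim is only 0.020. But an unknown ICC argues for a variance estimate that is valid at any value; the planned one is right only at zero net correlation.

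**A reader might infer that the trial is underpowered.** The documents do not support that. The planned test holds 80% at 135 per arm up to an ICC of about 0.14 and gains power at negative values. Imputation may let more than 135 per arm contribute, although 150 is an upper bound.

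**A reader might also infer that the error rate is certainly inflated, or that every comparison is affected.** The sign of the correlation is not known. Arm 2 against control should be little affected, since no contact between members is described in either arm.

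**Conclusion.** The concern holds in conditional form and should be fixed; it is not fatal. The plan assigns in threes, links members in two arms, and models only repetition within a participant. Its unconditional 80% power and 0.05 familywise statements therefore assume independence between participants without saying so.

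The main consequence is test size. At assumed ICCs of 0.05 to 0.20 the excess over 0.017 is modest against control and reaches about 2.6 times nominal (0.044 / 0.017) for arm 3 against arm 4. The FWER figures are not upper bounds, because correlation in arms 1 and 2 would raise them. Correlations of opposite sign cannot be relied on to cancel. All figures rest on normal approximations, a common SD of 2000, equal arms and an ICC range that the documents do not supply.

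**What to change.** **Section 9, analysis.** Keep the mixed model and add: *Standard errors for all phase 1 and phase 2 comparisons will be clustered on the assigned group of three. The clustered variance is the within-imputation variance in Rubin's rules, with a t reference based on the number of groups in the two arms compared* (50 + 50 − 2, about 98 complete-data degrees of freedom). This is valid for either sign of correlation. A group random intercept can serve as a sensitivity analysis, because it cannot represent negative correlation. Adding group membership to the imputation model is optional.

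**Sections 5.4 and 9, planning.** State that the 80% power assumes independence within groups. Give the group-adjusted power for arms 3 and 4 against control over an assumed range: about 80 / 78 / 74% at ICC 0.05 / 0.10 / 0.20 with 135 per arm and random dropout (1 to 2 points lower with the t reference, higher if imputation lets all 150 contribute). Make the familywise sentence conditional on group-clustered standard errors.

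**Cost.** One variance option and a few sentences. No new data are needed, since group membership is set at randomisation. At ICC 0 the t reference costs about 1 point of power (81.6% to 80.3%), and the stated power for arms 3 and 4 becomes slightly less favourable.

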### *3.2 Secondary outcomes*

Secondary outcomes include the proportion of participant-days that step goals are achieved during the intervention and follow-up periods, and change in daily steps from baseline to the follow-up period.

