### **--Goal Setting--**

Each participant will be asked to choose a step goal increase that is either 33%, 40%, or 50% higher than baseline (each step goal will be rounded up to the nearest hundred). A participant may also select to choose another goal as long as it is at least 1500 steps greater than his or her baseline.

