### *8.2 Procedures*

After providing informed consent, participants will complete an online questionnaire to determine their eligibility and complete the study surveys. Eligible participants will be mailed a wearable activity tracking device to wear a two week run-in period to collect a baseline step count.

Participants will select step goals and then be randomly assigned as described in the Study Design section.

We will obtain additional information about characteristics and behaviors of participants from the KBM Group, a data analytics firm. Participants will provide consent for the study team to send KBM Group their name and address using secure data transfer methods.

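### The goal-attainment analysis does not commit to adjusting for the goal increase chosen before randomisation; naming it costs nothing and may add precision

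*Combined protocol and SAP*

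**What the plan says.** Section 3.2 makes "the proportion of participant-days that step goals are achieved during the intervention and follow-up periods" a secondary outcome.

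Section 5.1 (Goal Setting) asks each participant to "choose a step goal increase that is either 33%, 40%, or 50% higher than baseline", rounded up to the next hundred, and adds: "A participant may also select to choose another goal as long as it is at least 1500 steps greater than his or her baseline". It states no upper limit.

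The goal comes before assignment in all arms. Section 5.1 (Randomization) treats participants as ready only once they have "completed all surveys, established a baseline step count, and selected a step goal increase", and section 8.2 confirms the order: "Participants will select step goals and then be randomly assigned as described in the Study Design section". Stratification is on three bands of baseline steps and on nothing else.

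Section 9 gives one model description, covering the physical activity outcomes in general. It adjusts for baseline steps and for "time at the observation level using calendar month fixed effects, participant random effects, and adjusting for repeated observations of participant step counts". It then plans further models with additional covariates, offering participant characteristics as an example. The chosen goal appears in neither list. No separate model or effect scale is given for the daily yes/no attainment outcome.

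Under the heading for arms 2 to 4, section 5.1 lets participants at the two lowest levels readjust their goals at weeks 8 and 16.

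**The concern.** A day counts as achieved or not against the participant's own goal, so the size of the chosen increase enters the outcome by definition. Two people with the same baseline and the same later walking can have quite different attainment because one chose a harder goal. This variation between participants is known before assignment and recorded for everyone, and the design does not balance it. If the model ignores it, it stays in the residual variation, together with any chance imbalance in chosen goals between arms. What is at stake is precision and power for one secondary outcome. The primary outcome is not affected.

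**Working it through.** **1. The plan's own figure.** Section 5.4 gives a difference of 800 steps, SD 2000, two-sided alpha 0.017, 80% power, 10% dropout and 600 participants in total.

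- n per arm = 2(z₀.₉₉₁₅ + z₀.₈₀)² × (2000/800)² = 2 × (2.387 + 0.842)² × 6.25, about 130.3, so 131.
- With dropout: 131/0.9 = 145.6, so 146 per arm and 4 × 146 = 584, in line with 600.
- With 150 × 0.9 = 135 completers per arm, power is 0.816.

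The stated size reproduces. It concerns daily steps; the documents give no power for goal attainment.

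**2. Does baseline already stand in for the goal?** Only in part. Applying the Goal Setting rules:

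| Baseline | 33% goal | 40% goal | 50% goal | Own goal from |
|---|---|---|---|---|
| 3,000 | 4,000 | 4,200 | 4,500 | 4,500 |
| 6,000 | 8,000 | 8,400 | 9,000 | 7,500 |
| 10,000 | 13,300 | 14,000 | 15,000 | 11,500 |

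At a baseline of 6,000 the 33% and 50% goals differ by 1,000 steps, more than the 800-step design difference. The 1,500-step minimum applies only to the own-goal option. Below about 4,500 steps the 33% option gives a smaller increase (1,500/0.33 is about 4,545).

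**3. Size of the gain, by simulation.** Taken from the plan: an 800-step arm effect, 135 per arm, 20 weeks × 7 = 140 days, alpha 0.017. Assumed, not in the documents:

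- baseline mean 7,000, SD 2,300;
- average change of 500 steps without intervention, with between-person SD 1,500 or 2,000;
- day-to-day SD 2,500 or 3,500;
- goal shares of 50/30/20% for the three preset options, or 40/25/20% with the remaining 15% choosing an 80% increase;
- correlation of 0, 0.3 or 0.5 between the latent tendency to choose a higher goal and later change in steps.

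The daily chance of attainment is 1 − Φ((goal − personal mean)/day-to-day SD). Each participant's attainment proportion was regressed on arm and baseline, then on arm, baseline and goal increase. The table gives the variance of the arm effect in the second model relative to the first, averaged over 300 runs, as the range across the four SD combinations.

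| Goals chosen | Correlation 0 | 0.3 | 0.5 |
|---|---|---|---|
| 33/40/50% only | 0.936–0.969 | 1.000–1.005 | 0.975–0.996 |
| 15% choose an 80% increase | 0.784–0.890 | 0.874–0.961 | 0.932–0.993 |

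The largest reduction is 1 − 0.784 = 0.216, about 22%; the smallest is none. Ratios just above 1 are about what one lost degree of freedom costs (267/266 = 1.004). Power moved by between −1 point (0.823 to 0.813) and +8 points (0.620 to 0.700). With 300 runs, a single power figure near 0.7 has a standard error of √(0.7 × 0.3/300) = 0.026, so small changes are noise.

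The gain vanishes with preset goals and a modest positive correlation because two effects cancel: a higher goal is harder to meet, but it also marks someone who will walk more.

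**4. A second set of assumptions.** Baseline mean 6,500, SD 2,000; day-to-day SD 3,000; own goals uniform from 1,500 to 5,000 steps above baseline.

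- Change SD 2,000, no correlation, 5% to 20% setting their own goal: residual variance falls by 4.9% to 9.1%.
- Change SD 2,000, correlation +0.2, 0% to 20% setting their own goal: about 0.4% to 4%.
- Change SD 1,500 to 2,500, correlation −0.2 to 0.2: 0.7% to 22%.

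**5. Readjusted goals.** The figures above hold goals fixed. A deliberately strong variant at zero correlation moved everyone below 4/7 attainment to the 33% goal at week 8. The gain fell from about 4–10% to 0.3–1.0%.

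**The case against.** The strongest reply has four parts.

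- **The covariate is not excluded.** A baseline goal choice would fit the open-ended list for the further adjusted models. A reader might infer that those models are confined to participant characteristics, but the text gives these only as an example. What remains is that nothing commits the sponsor to the goal term.
- **There is no separate attainment model to criticise.** The general description is framed as change from baseline, which a daily yes/no outcome does not have. That is fair. Still, it is the only description available, and the missing model and effect scale are a further reason to specify them.
- **Precision depends on the scale.** In a logistic mixed model, adding a prognostic covariate changes the conditional odds ratio and need not shrink its standard error. This stands, so the gain should be read as power or on the risk-difference scale, as in the calculations above.
- **The size is assumed, and readjustment erodes it.** This also stands. If days are scored on the current goal, the original increase is no longer the threshold for participants who readjust. The covariate also does not deal with a threshold that, as described, can move after randomisation in three arms only.

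Two stronger readings are tempting. One is that omission biases the comparison. It does not: goals are fixed before assignment, and ordinary standard errors already allow for chance imbalance. The other is that precision is certainly lost, by some 5% to 9%. That figure needs zero correlation between choice and later change and a particular share of own goals, and the documents establish neither.

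**Conclusion.** The point holds as a minor, free improvement. The plan collects before randomisation the variable that sets the threshold for its first-listed secondary outcome, does not balance it by stratification, and does not commit to adjusting for it. The comparison is valid either way.

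The possible gain is a reduction of about 0% to 22% in between-participant variance in attainment. It rests on assumed baseline and step variability, goal shares and the correlation between choice and later change. It is largest when goals vary widely and are unrelated to later change. It is near zero when few set their own goal and choice tracks later change, or when many in arms 2 to 4 readjust. The primary outcome, sample size and error control are not touched.

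**What to change.** In section 9, state the model for goal attainment and include the randomisation-time goal increase as a fixed covariate alongside baseline steps. Define it as selected goal minus baseline steps, in steps. Use that value for everyone, including those who later readjust, because a readjusted goal is a post-randomisation variable. Report the arm effect as a difference in attainment proportion (risk difference). Leave the primary daily-steps model unchanged.

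The cost is one prespecified covariate. The value is already held for every randomised participant, since choosing a goal is a condition of randomisation, so no new data are needed. At worst the gain is nil and one degree of freedom is spent. Prespecifying also removes a later choice about whether to adjust for the goal.
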